### 8.2.6.6. Moticon Digital Insole Device Sub-Study for Gait Assessments

Only study sites selected for participation in the Moticon sub-study for gait assessments using the digital insole device will perform the Moticon-related procedures at the time points according to [Table 1](#). This sub-study will enroll approximately 13 patients per treatment group to obtain

data on at least 10 patients per treatment group for a total of approximately 30 patients across the entire sub-study. For details on these procedures, participating sites will be provided with a Moticon digital insole device manual.

The principle purpose of this sub-study is to assess functional mobility gait parameters as measured by the Moticon insole device in patients with pain due to OA of the knee without an analgesic treatment and in the presence of potential analgesic treatment. The study will also examine correlations of these gait parameters with the WOMAC pain subscale score.

## **9. SAFETY DEFINITIONS, REPORTING, AND MONITORING**

### **9.1. Obligations of Investigator**

The investigator must promptly report to the Institutional Review Board (IRB)/EC all unanticipated problems involving risks to patients, according to local regulations. This may include death from any cause and all serious adverse events (SAEs) related to the use of the study drug. It is recommended that all SAEs be reported to the IRB/EC, according to local regulations.

### **9.2. Obligations of Sponsor**

During the course of the study, the sponsor will report in an expedited manner all SAEs that are both unexpected and at least reasonably related to the study drug (suspected unexpected serious adverse reaction [SUSAR]), to the health authorities, IECs/IRBs as appropriate, and to the investigators (in a blinded manner).

Any AE not listed as an expected event in the Reference Safety Information section of the Investigator's Brochure will be considered as unexpected. Any worsening of or new onset of symptoms related to OA that occur during the screening period prior to study drug administration will be considered expected.

In addition, the sponsor will report in an expedited manner all other SAEs to the health authorities, according to local regulations.

At the completion of the study, the sponsor will report all safety observations made during the conduct of the study in the clinical study report to health authorities and IECs/IRB, as appropriate.

### **9.3. Definitions**

#### **9.3.1. Adverse Event**

An AE is any untoward medical occurrence in a patient administered a study drug which may or may not have a causal relationship with the study drug. Therefore, an AE is any unfavorable and unintended sign (including abnormal laboratory finding), symptom, or disease which is temporally associated with the use of a study drug, whether or not considered related to the study drug.

An AE also includes any worsening (ie, any clinically significant change in frequency and/or intensity) of a pre-existing condition that is temporally associated with the use of the study drug.

### 9.3.2. Serious Adverse Event

An SAE is any untoward medical occurrence that at any dose:

- Results in **death** – includes all deaths, even those that appear to be completely unrelated to study drug (eg, a car accident in which a patient is a passenger).
- Is **life-threatening** – in the view of the investigator, the patient is at immediate risk of death at the time of the event. This does not include an AE that, had it occurred in a more severe form, might have caused death.
- Requires inpatient **hospitalization** or **prolongation of existing hospitalization**. Inpatient hospitalization is defined as a hospital admission (any duration) or an emergency room visit for longer than 24 hours. Prolongation of existing hospitalization is defined as a hospital stay that is longer than was originally anticipated for the event, or is prolonged due to the development of a new AE, as determined by the investigator or treating physician.
- Results in persistent or significant **disability/incapacity** (substantial disruption of one's ability to conduct normal life functions).
- Is a **congenital anomaly/birth defect**
- Is an **important medical event** – Important medical events may not be immediately life-threatening or result in death or hospitalization, but may jeopardize the patient or may require intervention to prevent one of the other serious outcomes listed above (eg, intensive treatment in an emergency room or at home for allergic bronchospasm; blood dyscrasias or convulsions that do not result in hospitalization; or development of drug dependency or drug abuse).

Criteria for reporting SAEs must be followed for these events. See Section 9.4 for more information on recording and reporting SAEs.

### 9.3.3. Adverse Events of Special Interest

An adverse event of special interest (AESI; serious or non-serious) is one of scientific and medical concern specific to the sponsor's product or program, for which ongoing monitoring and rapid communication by the investigator to the sponsor can be appropriate. Such an event might warrant further investigation in order to characterize and understand it. Depending on the nature of the event, rapid communication by the trial sponsor to other parties (eg, regulators) might also be warranted (Section 9.4.3).

### 9.3.4. Infusion Reactions

Infusion reactions are defined as any relevant AE that occurs during the infusion or within 2 hours after the infusion is completed. All infusion reactions must be reported as AEs (defined in Section 9.4.1) and graded using the grading scales as instructed in Section 9.5.1.

## 9.4. Recording and Reporting Adverse Events

### 9.4.1. Adverse Events

The investigator (or designee) will record all AEs that occur from the time the informed consent is signed until the end of the follow-up period.

Information on follow-up for AEs is provided in Section 9.4.6. Laboratory, vital signs, or ECG abnormalities are to be recorded as AEs as outlined in Section 9.4.5.

### 9.4.2. Serious Adverse Events

All SAEs, regardless of assessment of causal relationship to study drug, must be reported to the sponsor (or designee) within 24 hours.

Information not available at the time of the initial report must be documented in a follow-up report. Substantiating data such as relevant hospital or medical records and diagnostic test reports may also be requested.

In the event the investigator is informed of an SAE after the patient completes the study, the following will apply:

- SAE with an onset within 30 days of the end of the follow-up period or within 226 days of last study drug administration if the patient early terminated from the study - the SAE will be reported to the sponsor. The investigator should make every effort to obtain follow-up information on the outcome until the event is considered chronic and/or stable.
- SAE with an onset day greater than 30 days from the end of the follow-up period/early termination visit - only fatal SAEs and those deemed by the investigator to be drug-related SAEs will be reported to the sponsor. The investigator should make every effort to obtain follow-up information on the outcome of a drug-related SAE until the event is considered chronic and/or stable.
- SAE reported by the patient at the end-of-study phone call and deemed by the investigator to be drug-related will be reported to the sponsor. The investigator should make every effort to obtain follow-up information on the outcome of a drug-related SAE until the event is considered chronic and/or stable.

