#### **7.3.2. Study Drug Discontinuation**

Patients who permanently discontinue from study drug and who do not withdraw from the study will be asked to return to the clinic for all remaining study visits and to participate in all study phone calls per the visit schedule.

Patients who permanently discontinue from study drug and who opt to withdraw from the study will be asked to complete study assessments, per Section [8.1.3](#).

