### 8.1.3. Early Termination Visit

Patients who are withdrawn from the study before the primary endpoint visit (week 12) will be asked to return to the clinic for 2 visits: once for an early termination visit consisting of the early termination assessments described in [Table 1](#) and again at the primary endpoint visit (week 12), for studies with a primary efficacy endpoint. Patients who are withdrawn from the study after the primary endpoint visit will be asked to return to the clinic for early termination assessments, only.

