#### **9.4.6. Follow-up**

Adverse event information will be collected until the patient's last study visit.

Serious adverse event information will be collected until the event is considered chronic and/or stable.

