#### **4.5.1. Adverse Events and Serious Adverse Events**

Adverse event information is to be collected until the patient’s last study visit. Serious adverse event information is to be collected until the event is considered chronic and/or stable and/or resolved.

Adverse events (AE) and Serious Adverse Events (SAE) are collected from the time of informed consent signature and then at each visit until the end of follow-up visit (week 36) for AEs and until end of study visit (week 52) for SAEs. All AEs are to be coded to a “Preferred Term (PT)” and associated primary “System Organ Class (SOC)” according to the MedDRA® (the latest current available version).

An AE is any untoward medical occurrence in a patient administered a study drug which may or may not have a causal relationship with the study drug. Therefore, an AE is any unfavorable and unintended sign (including abnormal laboratory finding), symptom, or disease which is temporally associated with the use of a study drug, whether or not considered related to the study drug. An AE also includes any worsening (ie, any clinically significant change in frequency and/or intensity) of a pre-existing condition that is temporally associated with the use of the study drug. Laboratory results, vital signs, or ECG abnormalities are to be recorded as AEs if they are medically relevant: symptomatic, requiring corrective therapy, leading to treatment discontinuation and/or fulfilling a seriousness criterion.

An SAE is an AE that is classified as serious according to the criteria specified in the protocol. SAEs with an onset within 30 days of the end of the follow-up period or within 226 days of last study drug administration if the patient early terminated from the study is to be reported to the sponsor. SAEs with an onset day greater than 30 days from the end of the follow-up period/early termination visit: only fatal SAEs and those deemed by the investigator to be drug-related SAEs are to be reported to the sponsor. SAEs reported by the patient at the end-of-study phone call and deemed by the investigator to be drug-related are to be reported to the sponsor.

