## 5. STATISTICAL METHODS

For continuous variables, descriptive statistics include the following: the number of patients reflected in the calculation (n), mean, median, standard deviation (SD), minimum, maximum, and the first and third quartiles (Q1 and Q3).

For categorical or ordinal data, frequencies and percentages are displayed for each category.

Unless otherwise specified, table content is to be presented sorted by descending order of frequency of system organ class for the REGN5069 1000 mg group.

**Study Observation Period** – Unless otherwise stated, analysis of all safety and non-safety variables captured at multiple visits are to be analyzed by the following observations periods:

- *The Pre-Treatment Period* is defined as the time from signing the ICF to before the first dose of study drug.
- *The Treatment Period* is defined as the days from first dose of study drug to the day of last dose + 28 days (4 weeks). Summaries for the Treatment Period are based on the SAF.
- *The Follow-Up Period* is defined from the end of the Treatment Period to the Week 36 Visit/Early Termination Visit, regardless of the patient having completed the treatment period (week 12 visit) or not.
- *The Post-Follow-Up Period* is defined from the end of the Follow-Up Period to the phone call/Early Termination Visit.

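### For early terminators, the first two late-SAE rules in Protocol 9.4.2, repeated in SAP 4.5.1, give opposite instructions for non-fatal SAEs judged unrelated, with no stated precedence (minor)

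*Protocol*

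**What the plan says.** Protocol 9.4.2 opens by requiring that every SAE go to the sponsor, whatever its causality. It then sets three rules for SAEs that reach the investigator after the patient's participation is over:

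- **Rule 1.** Report any SAE with onset in the 30 days after follow-up ends, or "within 226 days of last study drug administration if the patient early terminated from the study". There is no restriction by outcome or causality.
- **Rule 2.** "SAE with an onset day greater than 30 days from the end of the follow-up period/early termination visit - only fatal SAEs" and those the investigator judges drug-related are reported.
- **Rule 3.** An SAE mentioned at the end-of-study phone call is reported if judged drug-related.

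SAP 4.5.1 carries the same three rules, with rule 2 as "SAEs with an onset day greater than 30 days from the end of the follow-up period/early termination visit: only fatal SAEs" plus drug-related ones. It also says that SAEs are collected "until end of study visit (week 52) for SAEs".

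Two other sections affect which days are exposed. Protocol 8.1.3 says that patients withdrawn "before the primary endpoint visit (week 12) will be asked to return to the clinic for 2 visits", the second being the week-12 visit. Protocol 9.4.6 says: "Adverse event information will be collected until the patient's last study visit".

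**The concern.** Rule 2 names the early termination visit, so it cannot be read as applying to completers only. Its clock starts at that visit, whereas rule 1's clock for the same patients starts at the last dose. The visit can come soon after the last dose, so the restricted rule can begin months before the full rule ends.

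On those days a non-fatal SAE judged unrelated must be reported under rule 1 and need not be under rule 2. A site that follows rule 2 as written would leave the sponsor without an event that rule 1 requires, and the sponsor could not then reassess its causality. Sites could also differ from one another. The protocol and SAP agree with each other on both rules, so reading one against the other does not settle it.

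**Working it through.** **Inputs.** Dosing is on nominal days 1, 29 and 57, and the week-12 and week-36 visits are on days 85 and 253 (Protocol Figure 1 note and Table 1). The limits of 226 and 30 days come from Protocol 9.4.2. L is the day of last dose and T the day of the early termination visit.

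**1. The 226-day figure.** The protocol gives no derivation, but the schedule reproduces it exactly: 253 + 30 - 57 = 226. For a patient who received all three doses, rule 1 ends on day 57 + 226 = 283. A completer's 30-day window ends on the same day, 253 + 30 = 283.

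**2. Overlap.** Rule 1 ends on day L + 226. Rule 2 starts on day T + 31. Both apply on

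(L + 226) - (T + 31) + 1 = 196 - (T - L) days, floored at 0.

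| L | T | Days under both rules | Length |
|---|---|---|---|
| 57 | 85 | 116-283 | 168 |
| 57 | 113 | 144-283 | 140 |
| 57 | 169 | 200-283 | 84 |
| 57 | 225 | 256-283 | 28 |
| 57 | 253 | none | 0 |
| 29 | 43 | 74-255 | 182 |

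On the nominal schedule, every patient with L = 57 who terminates before day 253 has some overlap.

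**3. Adjustment for the week-12 return visit.** If the patient in the last row attends the requested visit on day 85, ordinary AE collection runs to that day. The exposed days become 86-255, which is 170 days.

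**4. Effect on analysis outputs.** SAP Section 5 ends the Treatment Period at L + 28. Since T is not before L, the earliest conflict day is L + 31, so no treatment-emergent event is involved. The overall all-AE summaries in SAP 5.8.1 could change. The by-period SAE summaries could change only if the periods run past the early termination visit. On that the SAP is not uniform: Section 5 can end the Follow-Up and Post-Follow-Up Periods at that visit, while 5.8.1 runs follow-up AEs to Week 36.

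**The case against.** The strongest reply is that the intended rule can be recovered. The opening sentence of 9.4.2 calls for all SAEs. The Amendment 1 history says that the window for SAEs learned of after early termination was lengthened to 226 days on clinical pharmacology data. Step 1 also shows the figure lining up a fully dosed early terminator with a completer. On this view the mention of the early termination visit in rule 2 is leftover drafting. This stands as evidence of intent, but the current text states no precedence, and the late-SAE rules exist to qualify the opening sentence. A site applying rule 2 literally would not report.

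The reach is also small, and that stands:

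- Only SAEs learned of after the patient leaves the study are affected.
- Completers are not affected, and fatal or drug-related SAEs are reported under either rule.
- Patients with joint replacement up to week 36 return 4 and 20 weeks after surgery with AE collection (Protocol Table 2), so they have capture that the overlap formula ignores.
- SAP 1.2.4.2 ends the study after the Week 36 visits. Rule 1 can still run to day 283, so the conflict is not made empty.

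A reader might also infer two stronger points that the documents do not support.

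**A gap between the rules.** Protocol 7.3.2 says that patients who stop study drug "who do not withdraw from the study will be asked to return to the clinic for all remaining study visits", so T - L can exceed 196. With L = 29 and T = 245, rule 1's 226-day limit ends on day 255 and rule 2 starts on day 276, which appears to leave days 256-275 (20 days) uncovered. That holds only if the end of the follow-up period means week 36. SAP Section 5 allows that period to end at the early termination visit. The first part of rule 1 then covers T to T + 30, here days 245-275, and the gap closes. The overlap remains on either reading.

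**Week 52 as a third, unrelated SAE boundary.** Rule 3 in both documents already governs SAEs reported at the end-of-study call. What remains is that the SAP's collection sentence is not tied to that rule.

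**Conclusion.** The two rules contradict each other for early terminators in the current text of both documents. The conflict is confined to non-fatal SAEs judged unrelated with onset on days T + 31 to L + 226, a span of max(0, 196 - (T - L)) days per patient. These lengths assume nominal visit days and, except in step 3, no further study visit after early termination.

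The documents give no rate of early termination through week 36, so the number of patients or events cannot be estimated. It would be wrong to infer that the efficacy or treatment-emergent safety results are compromised. This is an internal inconsistency of minor severity, worth correcting because it bears on what sites send to the sponsor.

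**What to change.** Reconcile rules 1 and 2 so that early terminators have a single boundary, confirmed by the sponsor. Word it identically as the end of full reporting in rule 1 and the start of restricted reporting in rule 2, in both Protocol 9.4.2 and SAP 4.5.1. Align the SAP's week-52 SAE collection sentence with rule 3.

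If the sponsor confirms that the 226-day window is intended, one wording that works is the later of 226 days after last dose and 30 days after the early termination visit, that is, day max(L + 226, T + 30). For L = 57 and T = 85, full reporting ends on day 283 and restricted reporting starts on day 284. For L = 29 and T = 245, the boundary is day 275, so the question of a gap does not arise on either reading. No patient's full-reporting window becomes shorter.

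The cost is a short wording amendment, the IRB/EC approval that Protocol 14.4 requires for protocol amendments, a matching SAP edit, a site notification and slightly more SAE reports.

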### 9.4.3. Other Events that Require Accelerated Reporting to Sponsor

The following events also require reporting to the sponsor (or designee) within 24 hours of learning of the event:

**Symptomatic Overdose of Study Drug:** Accidental or intentional overdose of at least 2 times the intended dose of study drug within the intended therapeutic window, if associated with an AE.

**Pregnancy:** Although pregnancy is not considered an AE, it is the responsibility of the investigator to report to the sponsor (or designee), within 24 hours of identification, any pregnancy occurring in a female or female partner of a male, during the study or within 274 days (9 months) of the last dose of study drug. Any

complication of pregnancy affecting a female study patient or female partner of a male study patient, and/or fetus and/or newborn that meets the SAE criteria must be reported as an SAE. Outcome for all pregnancies should be reported to the sponsor.

**Adverse Events of Special Interest:** All AESIs, serious and non-serious, must be reported within 24 hours of identification using the same reporting process as for SAE reporting, per Section 9.4.2. No AESIs have been defined for this study.

#### **9.4.4. Reporting Adverse Events Leading to Withdrawal from the Study**

All AEs that lead to a patient's withdrawal from the study must be reported to the sponsor's Medical/Study Director within 30 days.

#### **9.4.5. Abnormal Laboratory, Vital Signs, or Electrocardiogram Results**

The criteria for determining whether an abnormal objective test finding should be reported as an AE include:

- the test result is associated with accompanying symptoms, and/or
- the test result requires additional diagnostic testing or medical/surgical intervention, and/or
- the test result leads to a change in dosing (outside of protocol-stipulated dose adjustments), discontinuation from the study, significant additional concomitant drug treatment, or other therapy

Contact the Medical/Study Director in the event the investigator feels that an abnormal test finding should be reported as an AE, although it does not meet any of the above criteria.

Repeating an abnormal test, in the absence of any of the above conditions, does not constitute an AE. Any abnormal test result that is determined to be an error does not require reporting as an AE.

Evaluation of severity of laboratory abnormalities will be assessed according to the scale outlined in Section 9.5.1.

#### **9.4.6. Follow-up**

Adverse event information will be collected until the patient's last study visit.

Serious adverse event information will be collected until the event is considered chronic and/or stable.

### **9.5. Evaluation of Severity and Causality**

#### **9.5.1. Evaluation of Severity**

The severity of AEs will be graded according to the following scale:

- **Mild:** Does not interfere in a significant manner with the patient's normal functioning level. It may be an annoyance. Prescription drugs are not ordinarily needed for relief of symptoms, but may be given because of personality of the patient.

- **Moderate:** Produces some impairment of functioning but is not hazardous to health. It is uncomfortable or an embarrassment. Treatment for symptom may be needed.
- **Severe:** Produces significant impairment of functioning or incapacitation and is a definite hazard to the patient's health. Treatment for symptom may be given and/or patient hospitalized.

If a laboratory value is considered an AE, its severity should be based on the degree of physiological impairment the value indicates.

### **Infusion Reactions**

The severity of infusion reactions will be graded according to the following scale (semi-colon indicates "or" within description of the grade):

- **Mild:** Mild transient reaction; infusion interruption not indicated; intervention not indicated.
- **Moderate:** Therapy or infusion interruption indicated but responds promptly to symptomatic treatment (eg, antihistamines, NSAIDs, narcotics, IV fluids); prophylactic medications indicated for  $\leq 24$  hours.
- **Severe:** Prolonged (eg, not rapidly responsive to symptomatic medication and/or brief interruption of infusion); recurrence of symptoms following initial improvement; hospitalization indicated for clinical sequelae; life-threatening consequences; urgent intervention indicated; death.

